6.2 Safety Variables

Safety will be assessed by evaluation of the following variables:

- Treatment-emergent adverse events (TEAEs; frequency, severity, seriousness, and relationship to study drug),
- Vital signs (systolic and diastolic blood pressure, pulse, respiratory rate and weight),
- Clinical laboratory variables (hematology, biochemistry including liver enzymes and total Bilirubin, and urinalysis),
- Physical examination,
- 12-lead electrocardiogram (ECG).
- Vascular Access Thrombosis

The **Safety Emergent Period** will be defined as the evaluation period from the Analysis date of first drug intake up to 28 days after the Analysis Last Dose date (defined in Section 6.5.4). Refer to Section 7.11.5 for more details on the derivation of the date of End of the Safety Emergent Period. This period will also be used to identify the minimum or maximum values collected on-treatment, defined as values collected from Day 2 up to the end of the Safety Emergent Period.

6.2.1 Adverse Events

6.2.1.1 Treatment emergent adverse event (TEAE)

TEAE is defined as an adverse event observed after starting administration of the test drug/comparative drug. If the adverse event occurs on Day 1 and the onset check box is marked “Onset after first dose of study drug” or the onset check box is left blank, then the adverse event will be considered treatment emergent. If the adverse event occurs on Day 1 and the onset check box is marked “Onset before first dose of study drug”, then the adverse event will not be considered treatment emergent. If a subject experiences an event both during the pre-investigational period and during the investigational period, the event will be considered as TEAE only if it has worsened in severity (i.e., it is reported with a new start date). Only adverse events starting during the Safety Emergent Period will be counted as TEAE .

A drug-related TEAE is defined as any TEAE with at least possible relationship to study treatment as assessed by the investigator or with missing assessment of the causal relationship.

Severity of AEs will be graded according to National Cancer Institute - Common Terminology Criteria for Adverse Events (NCI-CTCAE) Version 4.0.

For AE onset date imputation rules, refer to Section 7.11.2

All adverse events will be coded using the Medical Dictionary for Regulatory Activities (MedDRA) version 20.0.

6.2.1.2 Standardized MedDRA Queries

No standardized MedDRA Queries (SMQs) will be performed.

6.2.1.3 Time to occurrence of a TEAE (by type of AE group)

TEAEs are also classified into a number of groups depending on the following factors:

- Serious TEAEs
- Death during the Safety Emergent Period
- Any deaths (during the 24-month period)
- Related Serious TEAEs
- TEAEs Leading to permanent Discontinuation of the study drug
- TEAEs NCI CTC Grade 3 or Higher
- MedDRA System Organ Class (SOC)

The time to occurrence for a subject with a TEAE for a given type (except any deaths) will be calculated (in years) as:

$(\text{First TEAE date of the given type during the Safety Emergent Period} - \text{Analysis date of first dose intake} + 1) / 365.25$

With 'Analysis date of first dose intake' defined in Section [6.5.4](#) All adverse events collected during the Safety Emergent Period will be counted as TEAE, irrespective of use of rescue therapy.

Subjects who have not experienced a TEAE for that given type will be censored; the subject will be censored and the time to censoring for these subjects will be calculated (in years) as:

$(\text{Date of End of Safety Emergent Period} - \text{Analysis date of first dose intake} + 1) / 365.25$

With date of end of Safety Emergent Period defined in Section [7.11.5](#)

For any deaths during the 24-month period (including those occurring during the Post-Study Follow Up Period), time to occurrence for a subject who died during study / post study follow up) will be calculated (in years) as:

$[\text{End date for corresponding Fatal AE} - \text{Analysis date of first dose intake} + 1] / 365.25$

With 'End date for corresponding Fatal AE' which cover both study and post-study FU occurring up to Day 760 (i.e., month 24 + one month follow up + 3 days window as per protocol).

Subjects who have not died; the subject will be censored and the time to censoring for these subjects will be calculated (in years) as:

$\text{Minimum between } [\text{Day 760 and Max (Date of last known date when subject alive (End of Post-study FU), Date of last contact (Post study FU visit/call), Date of last Study evaluation (EOS form))} - \text{Analysis date of first dose intake} + 1] / 365.25$

Additional analyses censoring data post dialysis:

Time to occurrence with censoring all data at the initiation of permanent dialysis will be calculated as above where events occurring after initiation of dialysis will not be considered.

Subjects who initiated dialysis and who have not experienced an event prior to the dialysis will be censored and the time to censoring for these subjects will be calculated (in years) as:

$$(\text{Date of first dialysis} - \text{Analysis date of first dose intake} + 1) / 365.25$$

Subjects who have not experienced an event and did not initiate dialysis during the Safety Emergent Period, the time to censoring will be calculated (in years) as

$$(\text{Date of End of Safety Emergent Period} - \text{Analysis date of first dose intake} + 1) / 365.25.$$

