7.5.1.4 Incidence rates and cumulative incidence

Since the percentage of adverse events might be different between treatment arms due to the difference in the discontinuation rates, in addition to the frequency tables above, the incidence rate (per 100 subject years at risk) and the cumulative incidence at 6 months, 12,

18 months & 24 months with the 95% confidence interval, using Greenwood's formula, will be reported by treatment arm.

It will be done for each of the following event types of special interest:

- Serious TEAEs,
- TEAE for each SOC (>10% for a SOC in total SAF)
- Deaths occurring during the Safety Emergent Period,
- Any death (including post-study follow up period),
- Related serious TEAEs,
- AEs leading to discontinuation of study drug, and
- TEAE NCI CTC Grades 3 or higher.

Hazard ratios of each of the TEAE categories of special interest above will be computed by using Cox Proportional Hazards regression stratified on region and history of CV and adjusted on baseline Hb and baseline eGFR as continuous covariates. Hazard ratios (roxadustat as relative to placebo) and their 95% CI will be calculated for each TEAE category.

As a sensitivity analysis, the above analysis will be repeated using IPCW method (Appendix 10.7) for the following event types of special interest:

- Serious TEAEs,
- TEAE for each SOC (>10% for a SOC in total SAF)
- Deaths occurring during the Safety Emergent Period, and
- TEAE NCI CTC Grades 3 or higher.

A dot-and-forest plot will be produced showing each of the above TEAE categories on the y-axis. The incidence rates by treatment arm, the stratified Cox hazard ratios (roxadustat as relative to placebo) and their 95% CI will be shown on the x-axis.

In addition, cumulative incidence plots for subjects experiencing each of the TEAE categories above will be produced by treatment arm.

Incidence rate (per 100 subject years at risk) in each treatment arm by SOC and PT and the cumulative incidences by SOC will also be produced for the most common TEAEs ($\geq 5\%$ in total SAF). In addition, cumulative incidence plots of subjects experiencing at least one most common TEAEs in a SOC will be produced. A dot-and-forest plot will be produced showing each SOC in the y-axis and the incidence rates, the Cox hazard ratio and its 95% CI in the x-axis. The SOC will be sorted by the hazard ratio.

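### As written, SAP 6.2.1.3 dates deaths in the Safety Emergent Period at the start of the fatal adverse event, not at death

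*SAP*

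**What the plan says.** SAP section 6.2.1.3 sorts events into groups for time-to-event analysis. Two of the groups are mortality groups: "Death during the Safety Emergent Period" and a separate one that begins "Any deaths (during the 24-month period". The general formula is introduced by "The time to occurrence for a subject with a TEAE for a given type (except any deaths) will be calculated (in years) as", and its event date is "First TEAE date of the given type during the Safety Emergent Period". Only the any-deaths group is taken out of that formula. It has its own rule, whose event date is "End date for corresponding Fatal AE". No separate rule is given for safety-period deaths.

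Section 6.2.1.1 places TEAEs in time by when they begin: "Only adverse events starting during the Safety Emergent Period will be counted as TEAE".

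For the additional analysis censored at dialysis, section 6.2.1.3 reuses the same event date: time to occurrence "will be calculated as above where events occurring after initiation of dialysis will not be considered". A subject is censored at dialysis only if no event came first.

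Section 7.5.1.4 lists "Deaths occurring during the Safety Emergent Period" among the event types analysed by incidence rate, cumulative incidence at 6, 12, 18 and 24 months, and Cox hazard ratio. It lists the same event again for the IPCW sensitivity analysis. Section 7.5.1.5 includes it in the dialysis-censored repeat. Section 6.1.3.16, by contrast, dates a death in the ESRD-free survival endpoint at the date of death within the same period.

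**The concern.** A mortality analysis should date the event at death. If it uses the start of the fatal adverse event, a subject who falls ill, lives for some weeks and then dies is counted as dead throughout those weeks. Three outputs are affected.

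- **Incidence rate.** Under section 6.2.1.5 the denominator is the sum of each subject's time to event or censoring, so early dating shortens time at risk and raises the rate.
- **Cumulative incidence and Cox model.** Deaths shortly after a reporting time can be counted before it, and the ordering of events in the Cox and IPCW analyses can change.
- **Dialysis-censored repeat.** This analysis is meant to leave out deaths after dialysis starts. If the fatal event began before dialysis and the subject died on dialysis, the written rule keeps the death as a pre-dialysis event. In a non-dialysis CKD population, deterioration that leads to dialysis and then to death is a plausible sequence.

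The same death would also carry two different dates in two mortality analyses reported side by side.

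**Working it through.** **The plan's own figure.** The only number in this part of section 6.2.1.3 is the Day 760 cap on the any-deaths analysis. With the SAP's visit-day convention, 7 × 104 + 1 = 729; adding 28 days of follow-up and a 3-day window gives 729 + 28 + 3 = 760. It reproduces. The point does not depend on it.

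**Which rule applies to safety-period deaths.**
1. Section 6.2.1.3 lists safety-period deaths and any deaths as two groups.
2. The general formula exempts one of them, any deaths.
3. Safety-period deaths therefore take the first TEAE date.
4. Section 6.2.1.1 places a TEAE by its start, and the any-deaths rule names an end date where an end date is wanted. So the TEAE date is the start date.

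**Effect on one subject.** Formula from section 6.2.1.3: time = (event date − first dose date + 1) / 365.25, which for an event on study Day d is d / 365.25. The days below are assumed for illustration, all within the Safety Emergent Period: fatal TEAE starts Day 200, chronic dialysis starts Day 210, death Day 230.

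| Rule | Main analysis | Dialysis-censored repeat |
|---|---|---|
| As written (start of fatal TEAE) | event at 200/365.25 = 0.5476 y | event at 0.5476 y, since Day 200 precedes Day 210 |
| Date of death | event at 230/365.25 = 0.6297 y | censored at 210/365.25 = 0.5749 y |

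The shift is 30/365.25 = 0.0821 y. The date-of-death value equals what the any-deaths rule would give for the same subject, taking the end date of the fatal event as the date of death.

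**Range of the shift.** The documents give no onset-to-death interval, so these lags are assumptions:

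| Lag (days) | Shift = lag/365.25 (years) |
|---|---|
| 0 | 0 |
| 7 | 0.0192 |
| 14 | 0.0383 |
| 30 | 0.0821 |
| 60 | 0.1643 |

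**Share of on-dialysis deaths reclassified.** A death on dialysis becomes a pre-dialysis event when the lag exceeds the time from dialysis start to death. Assume an exponential lag with mean m days and dialysis starting uniformly within the w days before death. The share is then (m/w) × (1 − exp(−w/m)).

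- m = 3, w = 180: (3/180) × (1 − exp(−60)) = 0.017
- m = 14, w = 90: (14/90) × (1 − exp(−6.43)) = 0.155
- m = 30, w = 30: 1 × (1 − exp(−1)) = 0.632

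Simulation under the same assumptions gave the same values. The range of 1.7% to 63% shows mainly that the size cannot be fixed from the documents.

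**The case against.** The best reply is that the SAP never says onset. The date belonging to a group called death could naturally be read as the date of death. Other parts of the SAP support that intention: section 7.5.1.1 reports TEAEs leading to death separately from deaths in the Safety Emergent Period, section 6.1.3.16 uses the date of death, and section 7.11.5 uses it to help close the period. On that reading a Day 230 death after Day 210 dialysis is simply a post-dialysis event and is dropped.

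This shows what was probably meant, but it is not what the formula says: the formula asks for a TEAE date, and TEAEs are placed by their start. If the exemption for any deaths was instead meant to cover both mortality groups, safety-period deaths have no event date at all. Either way the text needs correcting.

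Two other parts of the reply stand in full. Section 7.5.1.4 already plans incidence rate, cumulative incidence and hazard ratio for any death, dated at the end of the fatal event; only the IPCW and dialysis-censored repeats leave that group out. And the shift is zero when the fatal event starts on the day of death.

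A reader might also infer that cumulative incidence of safety-period death above that of any death at the same time would be impossible, and so would prove a dating error. The documents do not support that. Both curves are one minus Kaplan-Meier and they censor differently: at the end of the Safety Emergent Period for one, at last contact or Day 760 for the other. Take four subjects with correct death dates: two leave the safety period at Day 40 and stay alive under follow-up, one dies on treatment at Day 100, one continues. At Day 100 the safety-period estimate is 1/2 and the any-death estimate is 1/4, with no dating error.

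**Conclusion.** The point holds on the text as written. Section 6.2.1.3 dates safety-period deaths at the start of the fatal TEAE, out of line with the any-deaths rule and with ESRD-free survival. Where onset and death differ, deaths move earlier in the section 7.5.1.4 analyses, and some deaths on dialysis can be kept as pre-dialysis events in the section 7.5.1.5 repeat.

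The conclusion rests on reading the TEAE date as a start date, which follows from section 6.2.1.1 and from the contrast with the explicit end date, but is not spelled out. The size rests on lags the documents do not give.

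It would be tempting to conclude that the hazard ratio for death is biased toward one arm. Nothing in the documents supports that: the lag may be similar in both arms, and no direction can be derived. Nor is mortality reporting as a whole compromised. The primary endpoints, the fixed testing sequence and the any-death analysis are untouched. This is a safety-analysis definition that should be corrected, not a threat to the trial's main conclusions.

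**What to change.** Add to SAP section 6.2.1.3, for the group of deaths in the Safety Emergent Period:

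- the event date is the date of death (the end date of the fatal adverse event), as for any deaths;
- that date must fall within the Safety Emergent Period;
- in the dialysis-censored version, the date of death is compared with the dialysis start date, so that a death after dialysis starts is censored at dialysis whenever the fatal event began.

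The cost is a short addition to the SAP and the matching change in the derivation of this one event time. No new data are needed, because the SAP already uses the date of death in sections 6.1.3.16 and 7.11.5.

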12.4 Appendix 4: Instructions for Subjects Requiring Dialysis

Subjects who initiate temporary or permanent dialysis treatment are allowed to continue in the study. All modes of dialysis, i.e., HD, hemodiafiltration (HDF) and peritoneal dialysis are allowed.

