7.5.1.3 Event-rates per 100 patient-years

The number of events and event rate (per 100 patient years) during the Safety Emergent Period with TEAEs, as classified by SOC and PT will be calculated by treatment arm. Summaries will be provided for:

- TEAEs
- TEAEs censored at start of chronic dialysis
- TEAE NCI CTC Grades 3 or higher
- Serious TEAEs,
- TEAEs leading to death.

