7.5.1.5 Sensitivity/Subgroup analyses

- Subgroups of interest :

The number and percentage of subjects reporting TEAEs in each treatment arm will be tabulated by SOC and PT for the subgroups of interest defined in Section 7.8

- Baseline eGFR category (< 15 vs ≥ 15) only :

The following summaries will be provided by comparing Baseline eGFR categories (< 15 vs ≥ 15) :

- Event rate per 100 patient-years for TEAEs by SOC and PT
 - Incidence rate and cumulative incidence for serious TEAEs
 - Incidence rate and cumulative incidence for deaths during the safety emergent period
 - Incidence rate and cumulative incidence for drug-related serious TEAEs
 - Incidence rate and cumulative incidence for AEs leading to discontinuation of study drug
 - Incidence rate and cumulative incidence for TEAE NCI CTC Grades 3 or higher
- Incidence rate and cumulative incidence censoring events occurring on or after the start of chronic dialysis :

The same analysis in incidence as described in Section 7.5.1.4 will be performed (i.e., incidence rate, hazard ratios, dot-and-forest plots and cumulative incidence plots) by censoring all data occurring at initiation of chronic dialysis (see Section 6.2.1.3 for more details regarding the definition of time to event and time to censoring) :

It will be done for :

- Serious TEAEs
- Serious TEAEs by baseline eGFR category (< 15 vs ≥ 15)
- Deaths occurring during the Safety Emergent Period,
- Deaths occurring during the Safety Emergent Period by eGFR category (< 15 vs ≥ 15)
- Drug-related serious TEAEs,
- Drug-related serious TEAEs by eGFR category (< 15 vs ≥ 15)
- AEs leading to discontinuation of study drug,
- AEs leading to discontinuation of study drug by eGFR category (< 15 vs ≥ 15)
- TEAE NCI CTC Grades 3 or higher
- TEAE NCI CTC Grades 3 or higher by eGFR category (< 15 vs ≥ 15)
- Incidence rate for TEAE by SOC and most common PTs
- Cumulative incidence by SOC for most common PTs.

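### The dialysis-censored safety sensitivity analysis is named for permanent or chronic dialysis, but its rule in SAP 6.2.1.3, read literally, censors at the first dialysis of any kind

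*SAP*

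**What the plan says.** SAP 6.2.1.3 gives the main time-to-event definitions for TEAEs and then adds an analysis that censors follow-up once dialysis begins. The opening clause sets the trigger as permanent dialysis: "Time to occurrence with censoring all data at the initiation of permanent dialysis will be calculated as above". The end of the same sentence has no qualifier: "events occurring after initiation of dialysis will not be considered". The operative rules follow:

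- **Who is censored early.** "Subjects who initiated dialysis and who have not experienced an event prior to the dialysis will be censored".
- **At what date.** The time-to-censoring formula uses "Date of first dialysis".
- **Who is followed on.** "Subjects who have not experienced an event and did not initiate dialysis during the Safety Emergent Period" are censored at the end of that period.

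No line covers a subject whose only dialysis was temporary.

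SAP 7.5.1.5 describes the same analysis as done "by censoring all data occurring at initiation of chronic dialysis" and refers to 6.2.1.3 for the event and censoring times. SAP 7.5.1.3 lists a related event-rate summary, "TEAEs censored at start of chronic dialysis".

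Protocol Appendix 4 (12.4) states: "Subjects who initiate temporary or permanent dialysis treatment are allowed to continue in the study". Section 12.4.1 keeps such subjects on study drug at their previous dose and frequency.

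**The concern.** The name of the analysis and its rule point to different dates. A programmer who follows the formula would censor at the first dialysis session of any kind. One who follows the name would censor only at the start of chronic dialysis. Both could publish tables under the same title.

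The outputs in 7.5.1.5 that depend on the rule are incidence rates, hazard ratios and cumulative incidence for serious TEAEs, deaths in the Safety Emergent Period, drug-related serious TEAEs, AEs leading to discontinuation and Grade 3 or higher TEAEs, each also by baseline eGFR below or above 15. Incidence by SOC and common preferred term depends on it too.

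The revision history gives the purpose of these analyses as assessing how dialysis affects AE incidence rates. If subjects who need an acute course are at higher risk afterwards, the literal rule removes follow-up in which events are more likely, while the subject is still on study drug and not on chronic dialysis.

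**Working it through.** There is no plan figure to reproduce. The check sets the texts side by side, applies the SAP's time formula to example subjects, and shows a range under assumed inputs.

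**Step 1. Does the SAP distinguish dialysis types?** Yes. Sections 6.1.2.8, 6.1.3.16 and 7.4.2.8 name acute and chronic dialysis together when both are meant. For time to a 40% eGFR decrease, 6.1.3.16 censors at the first occurrence of chronic dialysis and says so. The censoring rule in 6.2.1.3 does neither.

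**Step 2. Example subjects (hypothetical).** Time in years is (date − first dose + 1)/365.25, so study day d gives d/365.25. For a 104-week completer the last dose is on Day 728 (SAP Table 11), and the Safety Emergent Period runs at most to 728 + 28 = Day 756.

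| Subject | Rule as labelled | Rule read literally |
|---|---|---|
| Temporary dialysis Day 100, first serious TEAE Day 300, never chronic | Event at 300/365.25 = 0.821 y | Censored at 100/365.25 = 0.274 y, event not counted |
| Temporary dialysis Day 100, no event, completes | Censored at 756/365.25 = 2.070 y | Censored at 0.274 y; (756 − 100)/365.25 = 1.796 y lost |
| Acute course Day 100, chronic from Day 400, no event | Censored at 400/365.25 = 1.095 y | Censored at 0.274 y; (400 − 100)/365.25 = 0.821 y lost |
| First serious TEAE Day 50, temporary dialysis Day 100 | Event at 50/365.25 = 0.137 y | Same: the earlier event is kept |

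The third subject tests the milder reading. Suppose dialysis in the block is shorthand for chronic dialysis. This subject is then correctly among those censored, but the formula's date, taken at its word, is Day 100 and not Day 400.

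**Step 3. Possible size.** The documents give neither the number of temporary courses nor the event rate afterwards. The following were assumed: 600 subjects, 40 first events per 100 patient-years, all followed to Day 756 unless an event comes first, one temporary course at a uniformly distributed time in 2% to 10% of subjects, and the hazard after the course multiplied by 1, 2 or 4. Simulated results, scaled to 600 subjects:

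| With a course | Hazard multiple | Rate as labelled | Rate read literally | First events dropped | Time at risk removed |
|---|---|---|---|---|---|
| 2% | 1 | 39.98 | 39.99 | 2.9 | 0.9% |
| 2% | 4 | 40.54 | 39.98 | 6.3 | 0.5% |
| 5% | 2 | 40.70 | 40.01 | 11.5 | 1.7% |
| 10% | 1 | 39.97 | 39.97 | 14.6 | 4.3% |
| 10% | 4 | 42.79 | 39.97 | 31.1 | 2.3% |

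Rates are per 100 patient-years. With an unchanged hazard the rate hardly moves. The largest fall is 42.79 − 39.97 = 2.82, and it needs both the highest frequency and the highest multiple. The simulation has no treatment arms, so it says nothing about the hazard ratio.

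**The case against.** The best defence is that the opening clause fixes the scope. Having said permanent dialysis once, the SAP need not repeat it, and the later mentions refer back. The SAP also uses this shorthand elsewhere: in 6.1.3.16, the endpoint for chronic dialysis or transplant takes an unqualified date of dialysis as its event date. And where the SAP means any dialysis it tends to write acute or chronic, which 6.2.1.3 does not.

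This has some force, and the shorthand reading may be what was intended. It does not settle the formula. To match the label, the first-dialysis date would have to mean the first session of chronic dialysis, and 6.1.3.16 shows that the SAP spells that out when it wants it. The rule also never says what happens after a temporary course.

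Other objections limit the reach of the point, and they stand:

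- A reader might infer that every dialysis starter is censored. Only those with no earlier event of the type analysed are.
- A reader might infer that safety events disappear from the report. These are additional sensitivity outputs. The main analyses in 7.5.1.4 use the full Safety Emergent Period, and all data are listed.
- A reader might extend the point to the event rates in 7.5.1.3. Their denominator is Patient Exposure Years (6.2.1.6), not this time to censoring.
- A reader might take the version 5.0 entry that replaced time to first dialysis as proof that this rule was overlooked. That entry describes superseded text and concerns a different endpoint, so it proves nothing here.

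**Conclusion.** SAP 6.2.1.3 is inconsistent within itself and with 7.5.1.5. Read literally, the rule can give a result that differs from the title of the table: later follow-up and first events after a temporary course are lost. Even under the shorthand reading, an event-free subject with an acute course followed by chronic dialysis is censored too early if the formula's date is taken at its word.

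The point is confined to the dialysis-censored sensitivity analyses in 7.5.1.5. It touches no efficacy analysis and no main TEAE analysis. Its size cannot be stated from the documents. Under the assumed inputs above it ranges from about 3 to 31 first events dropped among 600 subjects, with a change in rate from about zero to 2.8 per 100 patient-years. Bias in the roxadustat-versus-placebo hazard ratio might be suspected, but the documents do not establish it. It would depend on how temporary courses and later risk differ between arms.

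**What to change.** In the dialysis-censoring block of SAP 6.2.1.3:

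1. Specify chronic dialysis in all three places where the rule now says only dialysis: the events to be ignored, the subjects censored early and the subjects followed on.
2. Replace the first-dialysis date in the formula with the start date of chronic dialysis used for the endpoints in 6.1.3.16.
3. Use one term for permanent and chronic in 6.2.1.3 and 7.5.1.5, and say how that status is identified in the data.
4. State that event-free subjects with temporary dialysis only are followed to the end of the Safety Emergent Period.

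If censoring at any dialysis was intended, keep the rule and relabel the analysis in 6.2.1.3 and 7.5.1.5 instead.

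The cost is one block of SAP text and one date variable. No new data are needed: the chronic dialysis date is already required for 6.1.3.16, and 7.11.2 already has an imputation rule for partial chronic dialysis dates. Reporting the number of subjects with temporary dialysis only, by arm, would show how much the choice matters.
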